## **2. ANALYSIS SETS**

### **2.1 Definition of analysis sets**

#### **2.1.1 Full analysis set**

All subjects enrolled in Studies D3461C00004 or D3461C00005 will be included in the main analysis of the LTE study, even if they do not enter the LTE study. Therefore, the full analysis set will consist of all subjects who were randomised and received at least 1 dose of investigational product in the Phase 3 feeder Studies D3461C00004 or D3461C00005. Subjects will be analysed according to the Intention-To-Treat principle (ie, as randomised). Subjects who withdraw consent to participate in the study will be included up to the date of their study termination.

Any major deviations from randomised treatment in the Phase 3 feeder studies or the LTE study will be listed and considered when interpreting the safety data.

#### **2.1.2 Full analysis set – LTE Study**

The full analysis set – LTE Study will consist of all subjects who were randomised and received at least 1 dose of investigational product in the LTE Study. Subjects will be analysed according to the Intention-To-Treat principle (i.e., as randomised). Subjects who withdraw consent to participate in the study will be included up to the date of their study termination.

#### **2.1.3 Safety analysis set**

The safety analysis set will comprise all subjects included in the full analysis set but with the treatment assignment based on the actual treatment received for  $\geq 50\%$  of doses in the LTE, which may differ from the randomly assigned treatment. If the safety analysis set is equivalent to the full analysis set, then the full analysis set will be used as the population description on the tables. If the safety analysis set is not equivalent to the full analysis set, key safety tables will be rerun using the safety analysis set. Any important deviations from randomised treatment will be listed and considered when interpreting the safety data.

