Although the study will initially be completely double-blind (ie, blind for subjects, Investigators/site staff, and Sponsor/designated clinical research organisation [CRO]), at the conclusion of the Phase 3 Studies D3461C00004 or D3461C00005 treatment allocation for all subjects who were previously on active treatment will become known to the Sponsor staff and/or designated CRO. The blind will be maintained for the Investigator and investigational site staff, for select roles at the CRO, and for the subjects. Further details are described in a separate unblinding plan.

In general, the first dose of study drug in the LTE study (LTE Day 1/Visit 1/Week 0) should occur on the same day as the final study visit of the prior study (ie, Week 52); however, special circumstances may warrant a delay in subject randomisation of up to 30 days following the final visit of the prior study (ie, Week 52). Administration of study drug in the LTE study should not occur until all LTE Day 1/Visit 1/Week 0 evaluations are completed.

This LTE study includes:

- **Treatment Period:** A 156-week treatment period with investigational product administered Q4W from LTE Week 0 to LTE Week 152 for a total of 39 doses. During the treatment period, visits will be scheduled for each Q4W administration.
- **At LTE Week 156 (or after the last dose of investigational product)** subjects will continue in the study for another 8 weeks to complete a 12-week safety follow up after the last dose of investigational product (last dose of investigational product will be given at LTE Week 152).

The total study duration will be up to approximately 164 weeks (including a 12-week Follow up Period after administration of the final dose).

Once subjects have completed Studies D3461C00004 or D3461C00005 (through Week 52), signed the informed consent form, and met all study eligibility criteria, they may be included in the LTE study.

In the event a site has not obtained the required approval (e.g., regulatory authority, local ethics committee) by the time a subject is eligible to be randomised in the LTE study, the site may be allowed the time to obtain the approval(s).

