#### 2.1.6 Treatment groups for analysis

Summaries will be presented according to the following combined treatment groups. If not mentioned otherwise, data from subjects discontinuing from the investigational product in studies D3461C00004 or D3461C00005, or who elect not to participate in the LTE, will be considered up to the adjusted analysis-defined visit window of Week 52 (ie, up to Day 378).

Primary:

- **Randomised Anifrolumab 300 mg:** Subjects randomised to anifrolumab 300 mg in studies D3461C00004 or D3461C00005 using all data from start of feeder study to end of LTE.
- **Randomised Placebo:** Subjects randomised to placebo in studies D3461C00004 or D3461C00005 using data from start of feeder study up until switch to anifrolumab 300 mg or to end of LTE for subjects re-randomised to placebo in LTE, respectively.

Supportive:

- **Placebo Feeder + Placebo LTE:** Subjects randomised to placebo in Studies D3461C00004 or D3461C00005 and re-randomised to placebo in LTE using all data from start of feeder study to end of LTE. Data from subjects not randomised into the LTE for any reason but that would have been re-randomised to placebo are included in this treatment group up to Week 52. Subjects who are not randomised into the LTE study will be assigned to Placebo or anifrolumab 300 mg via a

separate randomization process in order to determine who would have been re-randomised to placebo.

- **All Anifrolumab:** Subjects randomised to anifrolumab in studies D3461C00004 or D3461C00005, regardless of dose, and subjects randomised to placebo in studies D3461C00004 or D3461C00005 and then re-randomised to anifrolumab 300 mg in LTE, using all data from start of feeder study or switch to anifrolumab, respectively, to end of LTE. Baseline data from the feeder study will be included for all subjects.

Additional supportive:

- **Placebo Feeder + Anifrolumab 300 mg LTE:** Subjects randomised to placebo in studies D3461C00004 or D3461C00005 and then re-randomised to anifrolumab 300 mg in LTE using data from start of feeder study to end of LTE. Data from subjects not randomised into the LTE for any reason, but that would have been re-randomised to anifrolumab 300 mg are included in this treatment group up to Week 52. Subjects who are not randomised into the LTE study will be assigned to Placebo or anifrolumab 300 mg via a separate randomization process in order to determine who would have been re-randomised to anifrolumab 300 mg.

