## **4. ANALYSIS METHODS**

### **4.1 General principles**

#### **4.1.1 Data excluded from analysis**

In the rare event that a site needs to be closed during the course of the study for quality reasons (e.g., suspicion of fraud, non-compliance), all subjects of this site will be excluded from all analyses and summaries. In this situation, the SAP will be amended prior to database lock and details will be added documenting decisions about site closure and data handling (including details of important data to be presented in separate listings).

On 10-Feb-2017, the decision was made to close site [REDACTED] of Study D3461C00004 due to sustained noncompliance with protocol procedures and specifications. This included but was not limited to: failure to follow protocol stipulated inclusion/exclusion criteria, failure to maintain proper documentation in patient source files, and failure to maintain proper principal investigator oversight. The Site, FDA, and IRB have been notified of this site’s closure.

On 12-Jan-2018, the decision was made to close site [REDACTED] (in the LTE study as well as in Study D3461C00005) due to sustained noncompliance with protocol procedures and specifications. This included but was not limited to: lack of adherence to the blinding plan and delegation log by the unblinded pharmacist, and lack of adherence by the site study

coordinator and unblinded pharmacist to their roles and responsibilities for accountability of investigational product including reconstitution and preparation, leading to potential risk of unblinding study data. The Site, FDA, and IRB have been notified of this site's closure.

On 15-Mar-2021, the decision was made by AstraZeneca to exclude data from site [REDACTED] in the LTE study due to non-compliance to ICH E6 (R2) GCP section 8.1 addendum "The sponsor should ensure that the investigator has control of and continuous access to the CRF data reported to the sponsor. The sponsor should not have exclusive control of those data."

On 23 Nov 2021, the decision was made by AstraZeneca to exclude all data from site [REDACTED] in the LTE study since PRA ICON team decided that as the source documentation was destroyed /cannot be recovered as a result of a flood on site.

Therefore, the 20 randomised subjects [REDACTED]  
[REDACTED]  
[REDACTED]  

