### **4.2.1 Analysis of the primary variables (safety variables)**

If not stated otherwise, safety variables will be summarised by combined treatment group for the full analysis set.

The primary assessment will be the comparison between the treatment groups “Randomised Anifrolumab 300 mg” and “Randomised Placebo”. The “All Anifrolumab” treatment group will be used to assess rare events.

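### SAP 2.1.3 labels actual treatment by LTE doses alone, although the safety set holds every dosed feeder subject and its combined tables use feeder data

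*SAP*

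**What the plan says.** **Who is in the set.** The safety analysis set has the same members as the full analysis set, which SAP 2.1.1 defines as "all subjects who were randomised and received at least 1 dose of investigational product in the Phase 3 feeder Studies D3461C00004 or D3461C00005". Entry to the LTE is not required.

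**How treatment is assigned.** SAP 2.1.3 takes these subjects "but with the treatment assignment based on the actual treatment received for" at least 50% of "doses in the LTE, which may differ from the randomly assigned treatment". SAP 2.1.4 uses the same rule for the LTE-only safety set.

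**Which data are tabulated.** The combined groups in SAP 2.1.6 reach back to the feeder study. Randomised Anifrolumab 300 mg, for example, is built "using all data from start of feeder study to end of LTE". Every combined group is defined by randomised treatment. For feeder-placebo subjects who move to anifrolumab as planned, SAP 2.1.6, 3.1.1 and 3.3.4 split events and exposure at the switch.

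**When the set is used.** The main analysis is as randomised: "safety variables will be summarised by combined treatment group for the full analysis set" (SAP 4.2.1). Only if the two sets differ does 2.1.3 act: "key safety tables will be rerun using the safety analysis set". SAP 2.1.1 and 2.1.3 also provide for deviations from randomised treatment to be listed and weighed in interpretation.

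**The concern.** The LTE-dose rule suits a set restricted to LTE data. In 2.1.3 it is applied to a set whose records begin a year earlier and whose members need not have an LTE dose. Read literally, it leaves four gaps:

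- A feeder dosing error cannot change the label.
- A subject with no LTE dose has no label.
- An even split gives two labels.
- A feeder-anifrolumab subject who received mostly placebo in the LTE gets a placebo label, but both combined placebo groups are made up of subjects randomised to placebo in the feeder study.

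The SAP does not say what happens to feeder data in the last case, so the programmer would have to choose. The set exists to show safety by treatment received, and its tables are produced only when treatment received differed from treatment assigned. If the feeder year followed the LTE label, attribution in those tables could be less accurate than in the as-randomised ones. AESI counts are small, so one misplaced event can be visible.

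**Working it through.** **Inputs**
- LTE doses, SAP 1.2: "administered Q4W from LTE Week 0 to LTE Week 152 for a total of 39 doses". Check: 152/4 + 1 = 39, which reproduces the plan's figure.
- Feeder doses: SAP 4.2.3.1 puts the last feeder infusion at Week 48 (Visit 13). Four-weekly dosing from Week 0 is inferred: 48/4 + 1 = 13.
- Annual dropout of 20% (300 mg) and 30% (placebo), and 90% entry among completers: SAP 1.3. Applying these dropout rates to the feeder year is an assumption.
- Expected subject-years of 517 (Randomised Placebo), 893 (Randomised Anifrolumab 300 mg) and 1343 (All Anifrolumab): SAP 1.3.
- Number and pattern of dosing errors: not given. The range below runs from 1 to 39 LTE doses.

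**Step 1. Subjects with no LTE dose:** 1 − (1 − dropout) × 0.90.
- 300 mg: 1 − 0.80 × 0.90 = 28%.
- Placebo: 1 − 0.70 × 0.90 = 37%.

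**Step 2. Ties.** Any even number of LTE doses can split equally. With 38 doses, 19 and 19 satisfy the rule for both products.

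**Step 3. Anifrolumab time that could go to placebo.** Take a feeder 300 mg subject with 13 feeder doses and n LTE doses. Let w be the smallest number of placebo doses that reaches 50%, that is n/2 rounded up. If feeder data follow the LTE label, the true anifrolumab doses counted as placebo are 13 + (n − w), and the time is that number × 28/365.25 years.

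| LTE doses n | Placebo doses w | Anifrolumab doses / all doses | Share | Years |
|---|---|---|---|---|
| 1 | 1 | 13 / 14 | 93% | 1.00 |
| 13 | 7 | 19 / 26 | 73% | 1.46 |
| 26 | 13 (tie, taken as placebo) | 26 / 39 | 67% | 1.99 |
| 39 | 20 | 32 / 52 | 62% | 2.45 |

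**Step 4. Opposite direction.** Take a subject on placebo in the feeder study and re-randomised to placebo, who received mostly anifrolumab in the LTE. If the split at switch is applied, the feeder year stays out of anifrolumab. At most 19 LTE doses are misassigned: 19 × 28/365.25 = 1.46 years. Reaching one year takes 13 minority doses (13 × 28/365.25 = 1.00), so about 26 or more LTE doses in a near-even mix.

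**Step 5. Size against the tables.**
- Person-time per affected subject, at most: 2.45/517 = 0.47% of Randomised Placebo, or 2.45/893 = 0.27% of Randomised Anifrolumab 300 mg.
- Expected events at 1 per 1000 subject-years: 0.5 in Randomised Placebo and 1.3 in All Anifrolumab.
- One event moved into an empty placebo cell, holding 517 fixed: the rate goes from 0 to 1/517 = 1.9 per 1000, and the exact Poisson 95% upper limit from 7.1 to 10.8 per 1000.

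**Step 6. After assignment by period.** The feeder year can no longer be moved by LTE dosing errors. A 50% rule within the LTE can still misassign up to 19 of 39 doses (1.46 years).

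**The case against.** The strongest reply is that 2.1.3 nowhere says the feeder record moves with the LTE label. A reader might infer that it does, and conclude that a year or more of anifrolumab exposure will be counted as placebo. The documents do not support that as a statement of what the plan does. It is equally possible to let actual LTE treatment replace assigned LTE treatment and leave the feeder part in place, in which case the feeder year in Step 3 drops out. This stands, and 1.00 to 2.45 years is therefore a possible consequence of an unstated rule.

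Other points on that side also stand:
- The claim that placebo exposure will enter anifrolumab to the same extent is not supported. The split-at-switch rules largely protect that direction.
- Feeder dosing errors are not invisible. They are to be listed, although they cannot alter the label.
- SAP 4.1.1 describes a site closed over "responsibilities for accountability of investigational product including reconstitution and preparation", among other failings. A reader might take this as evidence of wrong product given. The text reports a possible risk to the blind and no actual misdosing, and subjects at the excluded sites appear only in sensitivity tables and key listings.
- The main safety analysis is untouched, and the share of person-time per affected subject is below 0.5%.

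It can also be argued that 2.1.3 implies a default to randomised treatment for subjects with no LTE dose, because it allows for the safety set to equal the full analysis set. That is a sensible guess at the intention, but it is not written. It also does not settle ties or the missing combined group.

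**Conclusion.** The point holds as a specification fault in a supporting analysis. SAP 2.1.3 applies an LTE-only rule to a set that spans both studies. It gives no label to subjects without an LTE dose (about 28% of 300 mg and 37% of placebo feeder subjects, on the Step 1 assumptions), no answer at a tie, and no combined group for feeder anifrolumab followed by mostly placebo. Until the handling of feeder data is stated, one such subject could put 1.00 to 2.45 years of true anifrolumab time into placebo. That range rests on 13 inferred feeder doses and on feeder data following the LTE label.

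The primary as-randomised results are not affected, and nothing in the documents shows that any subject received the wrong product. The consequence is limited to the conditional rerun of key safety tables, where its size depends on an unknown number of errors. The change is still worth making, because those tables are produced only when the rule has to work.

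**What to change.** In SAP 2.1.3, define actual treatment by period:

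- **Feeder events and person-time:** use the treatment actually received in the feeder study.
- **LTE events and person-time:** use the treatment actually received in the LTE, keeping the 50% rule and adding a stated rule for exact ties.
- **Subjects with no LTE dose:** label them by their actual feeder treatment.
- **Mapping:** assign each period to the 2.1.6 groups with the split at switch already used for planned switchers, and say where the LTE period of a feeder-anifrolumab subject with mostly placebo LTE doses is counted.

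Leave 2.1.4 as it is, apart from adding the tie rule.

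A split at the first anifrolumab dose ever received is not recommended as the general rule. One wrong kit at LTE Day 1 in a subject otherwise on placebo would move the other 38 true placebo doses into anifrolumab: 38 × 28/365.25 = 2.9 years.

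The cost is a few lines of SAP text and one derivation. A mis-dosed subject may contribute time to two groups, as planned switchers already do, and the residual misassignment within the LTE (Step 6) remains.

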#### 2.1.4 Safety analysis set – LTE Study

The safety analysis set – LTE Study will comprise all subjects included in the full analysis set – LTE Study but with the treatment assignment based on the actual treatment received for  $\geq$  50% of doses in the LTE, which may differ from the randomly assigned treatment. If the safety analysis set – LTE is equivalent to the full analysis set – LTE, then the full analysis set – LTE will be used as the population description on the tables. If the safety analysis set – LTE is not equivalent to the full analysis set – LTE, key safety tables will be rerun using the safety analysis set – LTE. Any important deviations from randomised treatment will be listed and considered when interpreting the safety data.

#### 2.1.6 Treatment groups for analysis

Summaries will be presented according to the following combined treatment groups. If not mentioned otherwise, data from subjects discontinuing from the investigational product in studies D3461C00004 or D3461C00005, or who elect not to participate in the LTE, will be considered up to the adjusted analysis-defined visit window of Week 52 (ie, up to Day 378).

Primary:

- **Randomised Anifrolumab 300 mg:** Subjects randomised to anifrolumab 300 mg in studies D3461C00004 or D3461C00005 using all data from start of feeder study to end of LTE.
- **Randomised Placebo:** Subjects randomised to placebo in studies D3461C00004 or D3461C00005 using data from start of feeder study up until switch to anifrolumab 300 mg or to end of LTE for subjects re-randomised to placebo in LTE, respectively.

Supportive:

- **Placebo Feeder + Placebo LTE:** Subjects randomised to placebo in Studies D3461C00004 or D3461C00005 and re-randomised to placebo in LTE using all data from start of feeder study to end of LTE. Data from subjects not randomised into the LTE for any reason but that would have been re-randomised to placebo are included in this treatment group up to Week 52. Subjects who are not randomised into the LTE study will be assigned to Placebo or anifrolumab 300 mg via a

separate randomization process in order to determine who would have been re-randomised to placebo.

- **All Anifrolumab:** Subjects randomised to anifrolumab in studies D3461C00004 or D3461C00005, regardless of dose, and subjects randomised to placebo in studies D3461C00004 or D3461C00005 and then re-randomised to anifrolumab 300 mg in LTE, using all data from start of feeder study or switch to anifrolumab, respectively, to end of LTE. Baseline data from the feeder study will be included for all subjects.

Additional supportive:

- **Placebo Feeder + Anifrolumab 300 mg LTE:** Subjects randomised to placebo in studies D3461C00004 or D3461C00005 and then re-randomised to anifrolumab 300 mg in LTE using data from start of feeder study to end of LTE. Data from subjects not randomised into the LTE for any reason, but that would have been re-randomised to anifrolumab 300 mg are included in this treatment group up to Week 52. Subjects who are not randomised into the LTE study will be assigned to Placebo or anifrolumab 300 mg via a separate randomization process in order to determine who would have been re-randomised to anifrolumab 300 mg.
- **Anifrolumab 150 mg Feeder + Anifrolumab 300 mg LTE:** Subjects randomised to anifrolumab 150 mg in Study D3461C00005 and then switched to anifrolumab 300 mg in LTE using data from start of feeder study to end of LTE. Data from subjects discontinuing from the investigational product in study D3461C00005, or who elect not to participate in the LTE are included in this treatment group up to Week 52.

[figure not shown]

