### 3. PRIMARY AND SECONDARY VARIABLES

If not stated otherwise, not only data collected during the LTE study but also data collected in the Phase 3 feeder Studies D3461C00004 and D3461C00005 will be considered. If not stated otherwise, all references to Day 1 and date of first dose of investigational product, respectively, refer to the respective day in the Phase 3 feeder studies. The date of last dose of investigational product refers to the last dose during the LTE study for subjects who started the LTE study and to the last dose in the Phase 3 feeder studies for subjects not continuing in the LTE study.

Baseline is defined as baseline of the Phase 3 feeder studies, i.e., the last non-missing measurement prior to dose administration on Day 1. If the Day 1 value is missing or is invalid or is collected after administration of investigational product, the latest assessment prior to dose administration on Day 1 will serve as baseline.

[REDACTED]

[REDACTED]

If not stated otherwise, change from baseline will be calculated as value at the respective post-baseline time point minus value at baseline.

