### 3.1.6 Laboratory variables

The parameters haematology, serum chemistry, urinalysis (outlined in Table 5 in Section 5.2.9 of the clinical study protocol), and fasting lipid profile (high density lipoprotein cholesterol, low density lipoprotein cholesterol, and triglycerides) will be explored.

Glucose (serum chemistry), cholesterol (serum chemistry), high density lipoprotein cholesterol (fasting lipid profile), low density lipoprotein cholesterol (fasting lipid profile), and triglycerides (fasting lipid profile) will only be considered in tables and figures if the subject fasted for at least 8 hours prior to the assessment.

Laboratory data will be reported in SI units. Changes from baseline in haematology, clinical chemistry, and lipid profile variables will be calculated.

Absolute values will be compared to the reference range [REDACTED] and classified as low (below range), normal (within range or on limits), or high (above range). All values (absolute and change) falling outside the reference ranges will be flagged.

Treatment-emergent laboratory/vital signs changes will be defined for post-baseline values according to the reference ranges [REDACTED]

Urinalysis data will be categorised as negative (0), trace, positive (+), or strongly positive (++, +++, or >+++)) at each time-point. Treatment-emergent changes will also be assessed.

[figure not shown]
Treatment-emergent changes of urinalysis data are defined as

[figure not shown]
- Negative/Trace/+ at baseline to ++, +++, +++++ at any post-baseline value OR
- Increase from baseline of at least ++ at any post-baseline value.

[figure not shown]
For the liver function tests: aspartate transaminase (AST), alanine transaminase (ALT), alkaline phosphatase, gamma glutamyl transferase (GGT), and total bilirubin, the multiple of

the upper limit of the normal (ULN) range [REDACTED] will be calculated for each data point. Multiple = Value / ULN, ie, if the ALT value was 72 IU/L (ULN = 36) then the multiple would be 2. Subjects meeting both of the following biochemical criteria for Hy's law (potential Hy's Law) at any point during the study (not necessarily at the same time) will be flagged:

[figure not shown]
- AST  $\geq 3x$  ULN and/or ALT  $\geq 3x$  ULN
- Total bilirubin  $\geq 2x$ ULN

[figure not shown]

[figure not shown]

[figure not shown]

[figure not shown]

[figure not shown]

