#### **4.2.1.6 Laboratory variables**

Observed values and changes from baseline of laboratory data for haematology, clinical chemistry, and fasting lipid profile will be summarised by visit. The summary statistics presented will be minimum, 1st quartile, median, 3rd quartile, maximum, mean, and SD.

Shift plots (scatter plots) presenting baseline values versus minimum post-baseline values (neutrophils, lymphocytes, monocytes, and haemoglobin only) and maximum post-baseline values (creatinine, creatinine kinase, blood urea nitrogen, alanine aminotransferase, aspartate aminotransferase, bilirubin), respectively, will be provided. A diagonal reference line indicating no change and horizontal and vertical reference lines indicating the limits of the reference ranges will also be displayed on the shift plots.

If any laboratory variables show any unusual features (high or low values or a general shift in the data points) at specific visits, then shift plots of these data may also be produced. This will be discussed and agreed upon during the BDR meeting.

[figure not shown]
For each laboratory parameter with available criteria, the number and percentage of subjects with TELVC values will be summarised by visit. Additionally, the number and percentage of subjects with at least 1 TELVC value will be presented. Percentages will be based on subjects with a measurement at baseline and at least 1 subsequent measurement of the variable (at the respective visit).

[figure not shown]
The number and percentage of subjects with laboratory values below, within, or above the corresponding reference ranges [REDACTED] will be presented as shift tables from baseline to maximum and minimum on-treatment value, respectively.

[figure not shown]
Urinalysis will be summarised as shift tables from baseline to the last on-treatment value for each parameter. Furthermore, the number and percentage of subjects with treatment-emergent changes will be summarised by parameter. Percentages for the summary of treatment-emergent changes will be based on subjects with a measurement at baseline and at least 1 subsequent measurement of the variable.

[figure not shown]
In order to identify potential Hy's Law cases, a shift table of maximum on-treatment total bilirubin against maximum on-treatment ALT, and maximum on-treatment AST expressed as multiples of ULN will be presented.

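### For placebo-to-anifrolumab switchers in All Anifrolumab, the shift tables and the urinalysis treatment-emergent table compare post-switch values with a baseline taken before the placebo year.

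*SAP*

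**What the plan says.** - **Baseline.** SAP section 3: "Baseline is defined as baseline of the Phase 3 feeder studies, i.e., the last non-missing measurement prior to dose administration on Day 1". The same section sets a default for dates: "all references to Day 1 and date of first dose of investigational product, respectively, refer to the respective day in the Phase 3 feeder studies". For a subject who spent the feeder year on placebo, that point precedes the placebo year. The lines that follow the definition are redacted.
- **Data window.** SAP 2.1.6 builds All Anifrolumab "using all data from start of feeder study or switch to anifrolumab, respectively, to end of LTE". Switchers therefore contribute post-baseline values only from the switch. The same entry ends: "Baseline data from the feeder study will be included for all subjects".
- **Tables affected.** SAP 4.2.1: "If not stated otherwise, safety variables will be summarised by combined treatment group for the full analysis set". All Anifrolumab is one of the combined groups. Laboratory shift tables run "from baseline to maximum and minimum on-treatment value" (4.2.1.6). Vital-sign shift tables use the maximum and minimum post-baseline values (4.2.1.2). ECG and urinalysis shift tables use the last on-treatment value (4.2.1.4, 4.2.1.6).
- **Urinalysis emergence.** The first limb of the rule in SAP 3.1.6 reads "Negative/Trace/+ at baseline to ++, +++, +++++ at any post-baseline value OR". The second limb is a rise of at least ++ over baseline.
- **Where the SAP does restart the clock.** For switchers in All Anifrolumab, adverse events with onset before the first LTE dose are left out. Event rates, time to first AESI, flare rates and exposure all start at the first LTE or anifrolumab dose (3.1.1, 3.1.5, 3.3.4).

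**The concern.** A shift or treatment-emergent table asks whether a value became abnormal after the drug was started. For switchers the reference value is about a year too early, and that year was spent on placebo. The table then mixes changes on placebo with changes on anifrolumab and reports both under anifrolumab. The SAP avoids this for adverse events, rates, flares and exposure by restarting at the switch, but shows no matching restart for measurements judged against baseline. All Anifrolumab is the group the SAP assigns to rare events, so its laboratory, vital-sign and ECG abnormality counts are likely to be read as experience on the drug.

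**Working it through.** The plan states no figure on this point, so there is nothing to reproduce. The check follows the rules through the SAP and then sizes the group affected.

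**Step 1: apply the visible urinalysis rule (SAP 3.1.6) to a switcher**

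| Case | Feeder baseline | Week 52 on placebo | After switch | Emergent with feeder baseline? | Emergent with pre-switch baseline? |
|---|---|---|---|---|---|
| A | Trace | ++ | ++ | Yes | No |
| B | ++ | Negative | ++ | No | Yes |
| C | Trace | ++ | Negative | No | No |

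- Case A: Trace to ++ meets the first limb. Against a pre-switch ++ neither limb is met. An abnormality from the placebo year is charged to anifrolumab.
- Case B: ++ to ++ meets neither limb. Against a pre-switch negative value the first limb is met. An abnormality that appeared on anifrolumab is missed.
- Case C: only post-switch values count for switchers, so an abnormality that cleared before the switch and did not recur does no harm.

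The shift tables work the same way. A value that moved from normal to out of range on placebo and stays there appears as a shift on anifrolumab.

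**Step 2: size of the switcher group**

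Inputs: about 575 LTE subjects (Protocol synopsis; SAP 1.2), anifrolumab to placebo about 4:1 in the LTE, and feeder placebo subjects re-randomised 1:1 (SAP 1.2).

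- LTE placebo = 575 / 5 = 115.
- Switchers = 115, by the 1:1 re-randomisation.
- LTE anifrolumab = 575 − 115 = 460.
- Switcher share = 115 / 460 = 25%.

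All Anifrolumab also contains subjects given anifrolumab in the feeder studies who never entered the LTE. Its denominator therefore exceeds 460 and the share is below 25%.

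**Step 3: upper bound on the upward error**

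The documents give no abnormality rates. Let m be the proportion of switchers with a new abnormality at Week 52 that is still present after the switch (assumed).

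Misattributed subjects = 115 × m. Error in percentage points is at most 100 × 115 × m / 460 = 25 × m.

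| m (assumed) | Subjects | Upper bound, points |
|---|---|---|
| 2% | 2.3 | 0.5 |
| 5% | 5.75 | 1.25 |
| 10% | 11.5 | 2.5 |
| 20% | 23 | 5.0 |

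These are upper bounds for two reasons: the true denominator is larger than 460, and missed cases of type B pull the other way.

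**The case against.** Several points on the other side stand.

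- **The sentence in 2.1.6 may be only a data-inclusion rule.** SAP 4.2.3.2 takes demography, medical history and prior medication from the feeder study and uses All Anifrolumab as its example. A reader might infer that the 2.1.6 sentence alone fixes the reference for shifts, but it need not. The point rests on the general definition in section 3.
- **Redaction.** An exception for switchers could sit in the lines removed after the baseline definition. The TELVC criteria are also removed. If they are absolute thresholds, a new baseline might not alter those counts. Wrongly counted emergence can be shown only for urinalysis; the effect on the shift tables follows from their visible description.
- **Direction.** A reader might infer steady inflation of abnormality frequencies. Case B shows that the error runs both ways, and the documents give no rates from which to net the two.
- **LTE-only tables.** A reader might infer that laboratory, vital-sign and ECG results for the LTE-only switch group are spoiled. SAP 4.1.3 provides for LTE-only tables in general, but 4.2.1.2 to 4.2.1.6 specify none for these variables.
- **Primary objective.** A reader might infer that AESI and SAE results are affected. They are not: placebo-year events are excluded by onset date and by the study in which they were recorded. In the primary comparison each group is measured from its own feeder baseline.
- **A common baseline is defensible for by-visit changes.** Visit windows label switchers' first LTE visits from Week 56. Re-baselining switchers alone would pool a 4-week change with a 56-week change in one column. This limits where the fix should apply.

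**Conclusion.** The point holds for a limited set of supportive tables. On the visible text, switchers in All Anifrolumab have post-switch values compared with a baseline from before the placebo year. This affects the laboratory, urinalysis, vital-sign and ECG shift tables, the urinalysis treatment-emergent table, and any TELVC criterion that depends on baseline. The upward error in All Anifrolumab is at most about 0.5 to 5 percentage points for an assumed carry-over of 2% to 20%, partly offset by missed cases. That range rests on the planned 575 subjects, the approximate 4:1 ratio and 1:1 re-randomisation; the carry-over rates are assumptions. The redactions mean that an exception cannot be ruled out.

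**What to change.** For placebo-to-anifrolumab switchers in All Anifrolumab, define baseline for the shift and treatment-emergent tables as the last non-missing value before the first LTE dose. Apply it also to any TELVC criterion that depends on baseline. Keep feeder Day 1 for demography, medical history, disease characteristics and by-visit change tables. If the redacted text already contains such a rule, a cross-reference in SAP 2.1.6 is enough.

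No new data are needed. Protocol section 4.1 lets the feeder Week 52 assessments serve as LTE Day 1, and Protocol Table 2 schedules vital signs, ECG, chemistry, haematology and urinalysis at that visit. The cost is a second baseline variable in the programming and a table footnote stating which baseline applies to whom.
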